11.2.2.3 Modified EBMT Response Criteria

Response	Criteria for Response ^a
----------	------------------------------------

CONFIDENTIAL

This document is confidential. Do not disclose or use except as authorized.

Complete Response (CR)	
Requires all of the following:
 
Disappearance of the original monoclonal protein from the blood and urine on at least two determinations for a minimum of six weeks by immunofixation studies.
 
<5% plasma cells in the bone marrow on at least two determinations for a minimum of six weeks.^b
 
No increase in the size or number of lytic bone lesions (development of a compression fracture does not exclude response).^c
 
Disappearance of soft tissue plasmacytomas for at least six weeks.

Near Complete Response (nCR)	
Requires the following:
 
Same as CR, but immunofixation studies continue to show presence of the monoclonal protein

Very Good Partial Response (VGPR)	
Requires the following:
 
≥ 90% reduction in serum M-protein plus urine M-protein level <100mg per 24 hours on at least two determinations for a minimum of six weeks.

Partial response (PR)	
PR includes participants in whom some, but not all, criteria for CR are fulfilled providing the remaining criteria satisfy the requirements for PR. Required all of the following:
 
≥50% reduction in the level of serum monoclonal protein for at least two determinations six weeks apart.
 
If present, reduction in 24-hour urinary light chain excretion by either ≥90% or to < 200 mg for at least two determinations six weeks apart.
 
≥50% reduction in the size of soft tissue plasmacytomas (by clinical or radiographic examination) for at least six weeks.
 
No increase in size or number of lytic bone lesions (development of compression fracture does not exclude response).^c

CONFIDENTIAL

This document is confidential. Do not disclose or use except as authorized.

Minimal response (MR)	
MR included participants in whom some, but not all, criteria for PR were fulfilled, providing the remaining criteria satisfied the requirements for MR. Required all of the following:
 
$\geq 25\%$ to 49% reduction in the level of serum monoclonal protein for at least two determinations six weeks apart.
 
If present, a ≥ 50 to 89% reduction in 24-hour light chain excretion, which still exceeds 200 mg/24 h, for at least two determinations six weeks apart.
 
$\geq 25\text{--}49\%$ reduction in the size of plasmacytomas (by clinical or radiographic examination) for at least six weeks.
 
No increase in size or number of lytic bone lesions (development of compression fracture does not exclude response).^c

No change (NC)	Not meeting the criteria for MR or PD.
Progressive disease (PD) (for participants not in CR)	
Requires one or more of the following:
 
$>25\%$ increase^d in the level of serum monoclonal paraprotein, which must also be an absolute increase of at least 5 g/L and confirmed on a repeat investigation.
 
$>25\%$ increase^d in 24-hour urinary light chain excretion, which must also be an absolute increase of at least 200 mg/24 h and confirmed on a repeat investigation.
 
$>25\%$ increase^d in plasma cells in a bone marrow aspirate or on trephine biopsy, which must also be an absolute increase of at least 10%.
 
Definite increase in the size of existing lytic bone lesions or soft tissue plasmacytomas.
 
Development of new bone lesions or soft tissue plasmacytomas (not including compression fracture).
 
Development of hypercalcemia (corrected serum calcium >11.5 mg/dL or 2.8 mmol/L not attributable to any other cause).

CONFIDENTIAL

This document is confidential. Do not disclose or use except as authorized.

	
Required at least one of the following:
 
Reappearance of serum or urinary paraprotein on immunofixation or routine electrophoresis confirmed by at least one follow-up and excluding oligoclonal immune reconstitution.
 
Relapse from CR
 
≥5% plasma cells in the bone marrow aspirate or biopsy.
 
Development of new lytic bone lesions or soft tissue plasmacytomas or definite increase in the size of residual bone lesions (not including compression fracture).
 
Development of hypercalcemia (corrected serum calcium >11.5 mg/dL or 2.8 mmol/L not attributable to any other cause)^e.

--	---

a Based on the criteria reported by Blade et al., 1998.

b Per Blade *et al.*, 1998, if absence of the monoclonal protein is sustained for 6 weeks it is not necessary to repeat the bone marrow except in participants with nonsecretory myeloma where the marrow examination must be repeated after an interval of at least 6 weeks to confirm CR.

c Per Blade *et al.*, 1998, skeletal X-Rays are not required for the definition of response, but if performed there must be no evidence of progression of bone disease (no increase in size or number of lytic bone lesions).

d It is suggested that the reference point for calculating any increase should be the lowest value of the preceding confirmed response (MR, PR or CR) or the baseline value if there is no previous confirmed response.

e Other clinical data may be requested by the IRC, as necessary, to assess the cause of the hypercalcemia.

11.2.3 Criteria for Molecular CR and Minimal Residual Disease (MRD) measurement

We will measure MRD in patients who achieve CR to determine the number of patients who are MRD negative vs MRD positive.

11.2.3.1 MRD by LymphoSIGHT (Adaptive Inc.)

MRD will be carried out according to the LymphoSIGHT™ method (Adaptive Inc, Seattle, WA) ⁶¹. Prior studies have compared this technique to the traditional MRD immunofluorescence technique, as previously reported ⁶² and showed that MRD by LymphoSIGHT is a sensitive method that can be used in future clinical practice.

For MM diagnostic samples, genomic DNA will be amplified using locus-specific primer sets for the immunoglobulin heavy-chain locus (IGH) complete (IGH-VDJH), IGH incomplete (IGH-DJH), and immunoglobulin κ locus (IGK). The amplified product will be subjected to sequencing, and the sequences and frequencies of the different clonotypes in the sample will be obtained. Myeloma gene rearrangements will be identified. Patients in whom a high-frequency myeloma clone (>5%) is not identified will be excluded from the MRD analysis. MRD will be assessed in patients with a high-frequency myeloma clone using the IGH-VDJH and IGK or IGH-VDJH, IGH-DJH, and IGK assays. Once the absolute amount of total cancer-derived molecules present in a sample will be determined, a final MRD measurement will be calculated, providing the number of cancer-derived molecules per 1 million cell equivalents. In cases in which 2 or more tumor clones existed, the clone with the highest MRD value will be reported. Molecular CR will be defined according to the International Myeloma Working Group (IMWG) consensus recommendations⁶³.

CONFIDENTIAL

This document is confidential. Do not disclose or use except as authorized.

11.2.4 Duration of Response and Endpoint Definitions

11.2.4.1 Duration of overall response

The duration of overall response is measured as the time from initiation of first response to first documentation of disease progression or death. Patients who have not progressed or died are censored at the date last known progression-free.

11.2.4.2 Duration of overall complete response

The duration of overall CR is progression or death. Patients who have not progressed or died are censored at the date last known progression-free.

11.2.4.3 Time to progression

Time to progression is defined as the time of randomization until progression. Patients who have died without evidence of progression are censored in the TTP analysis at the time of death and patients who are alive without progression are censored at the last disease assessment.

11.2.5 Progression-Free Survival

The secondary endpoint in this study, PFS is defined as the time from randomization to the disease progression or death from any cause. Patients who have not progressed or died are censored at the date last known progression-free.

11.2.6 Response Review

Central review of disease response assessments is not planned.

12. DATA REPORTING / REGULATORY REQUIREMENTS

Adverse event lists, guidelines, and instructions for AE reporting can be found in Section 7.0 (Adverse Events: List and Reporting Requirements).

12.1 Data Reporting

12.1.1 Method

The DFCI Office of Data Quality will collect, manage, and perform quality checks on the data for this study.

12.1.2 Responsibility for Data Submission

Investigative sites within DF/HCC or DF/PCC are responsible for submitting data and/or data forms to the Data Safety Monitoring Committee According to the schedule set by the Office of Data Quality.

Data should be entered within 14 business days of the corresponding visit and within 14 business days of the end of a cycle for any forms to be completed per cycle.

CONFIDENTIAL

This document is confidential. Do not disclose or use except as authorized.

12.2 Data Safety Monitoring

The DF/HCC Data and Safety Monitoring Committee (DSMC) will review and monitor toxicity and accrual data from this study. The committee is composed of clinical specialists with experience in oncology and who have no direct relationship with the study. Information that raises any questions about participant safety will be addressed with the Overall PI and study team.

The DSMC will review each protocol up to four times a year or more often if required to review toxicity and accrual data. Information to be provided to the committee may include: up-to-date participant accrual; current dose level information; DLT information; all grade 2 or higher unexpected adverse events that have been reported; summary of all deaths occurring with 30 days of intervention for Phase I or II protocols; for gene therapy protocols, summary of all deaths while being treated and during active follow-up; any response information; audit results, and a summary provided by the study team. Other information (e.g. scans, laboratory values) will be provided upon request.

13. STATISTICAL CONSIDERATIONS

13.1 Study Design/Endpoints

The proportion of patients who achieve progression free at 2 years will be compared to the rate published for the high risk SMM. By the Mayo Clinic model for risk factors, the median time to progression for patients with high risk SMM was only 1.9 years. Therefore, we assume that, a 2-years progression-free rate of 50% will not be considered promising and a true progression free rate of 70% or higher will be considered promising. A single-stage design will be employed with 39 eligible patients entered. If 24 or more of the 39 eligible patients are progression free at 2 years (observed rate of 62%), we will conclude that this treatment warrants further study. The probability of concluding that the treatment is effective if the true rate is 50% is 0.10 and is >0.9 if the true rate is 70%. Assuming a dropout rate of 5%, we will accrue 41 patients to the trial in order to have 39 eligible patients. The Type I and II error probabilities have been derived using exact binomial probabilities.

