RBC	red blood cell
RECIST	Response Evaluation Criteria in Solid Tumors
SAE	serious adverse event
SC	Subcutaneous
SD	stable disease
SmPC	Summary of Product Characteristics
$t_{1/2}$	terminal disposition half-life
TGI	tumor growth inhibition
T_{\max}	single-dose time to reach maximum (peak) concentration
UK	United Kingdom
ULN	upper limit of the normal range
US	United States
V_z	volume of distribution in the terminal phase
WBC	white blood cell
WHO	World Health Organization

CONFIDENTIAL

This document is confidential. Do not disclose or use except as authorized.

PROTOCOL SUMMARY

Study Title: Phase II Trial of the PD-1 Antibody Nivolumab in Combination with Lenalidomide and Low Dose Dexamethasone in Patients with High-Risk Smoldering Multiple Myeloma	
Phase: II	
Number of Patients: 41	
Study Objectives: Primary Objectives To determine the proportion of high risk smoldering multiple myeloma patients who are progression free at 2 years after receiving Nivolumab and lenalidomide+ dexamethasone combination therapy	
Secondary Objectives 
• To assess the response rate of the combination in these patients• To assess time to progression and progression free survival• To assess duration of response• To assess the safety of the combination• To examine molecular evolution of the tumor cells• To determine the role of immune cells in the progression of smoldering MM• To determine minimal residual disease (MRD)	
Overview of Study Design: This is a single arm phase II study using the combination of Nivolumab and lenalidomide + low dose dexamethasone in patients with high risk smoldering multiple myeloma. The study is designed to examine novel therapeutic immunotherapy combinations in patients with smoldering MM. The trial will include a safety run in of 10 patients. If three of the ten patients experience a serious, unexpected adverse event during their first cycle of therapy, the study will be suspended temporarily until further safety review.	

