1.1 Study Design

This is a phase II study using the combination of Nivolumab and lenalidomide + low dose dexamethasone in patients with high-risk smoldering multiple myeloma. The trial will include a safety run in of 10 patients. If three of the ten patients experience a serious, unexpected adverse event during their first cycle of therapy, the study will be suspended temporarily until further safety review. If any one of the study medications is permanently discontinued for any reason including toxicity, or FDA mandate, the patient may remain on the study at the discretion of the principal investigator.

** As of September 2017, the trial has been put on partial clinical hold by the Food and Drug Administration: all patients are to discontinue nivolumab indefinitely, and no additional patients will be accrued to the trial. Participants may elect to remain on lenalidomide/dexamethasone or lenalidomide therapy alone for disease control after discussion with the overall PI.

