1.2 Number of Patients

A total of 41 patients will be included on this study. Enrollment includes patients who receive the first day of therapy.

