5. TREATMENT PLAN

5.1 Treatment Regimen

Treatment will consist of 6 cycles of induction therapy followed by maintenance therapy for a total of 12 months. A treatment cycle is defined as 28 consecutive days.

For treatment cycles 1 through 12, a +/- 7 day window for nivolumab dosing is allowed. For further guidance on lenalidomide and dexamethasone holds and delays, please see Table 17. No investigational or commercial agents or therapies other than those described below may be administered with the intent to treat the participant's malignancy.

** As of September 2017, the trial has been put on partial clinical hold by the Food and Drug Administration: all patients are to discontinue nivolumab indefinitely, and no additional patients will be accrued to the trial. Participants may elect to remain on lenalidomide/dexamethasone or lenalidomide therapy alone for disease control after discussion with the overall PI.

Induction Cycles

Table 7: Nivolumab and Lenalidomide and Dexamethasone Combination (Cycles 1-6)

Agent	Pre-medications/ Precautions	Dose	Route	Schedule	Cycle Length
Nivolumab	None	240 mg	Intravenous	Days 1,15	28 days
Lenalidomide	None	25 mg	Oral	Days 1-21 of each cycle	
Dexamethasone	Take with food; Recommended to be taken in the morning	40 mg	Oral	Days 1, 8, 15	

Maintenance Cycles**

Table 8: Nivolumab and Lenalidomide Combination (Cycles 7-12)

Agent	Pre-medications/ Precautions	Dose	Route	Schedule	Cycle Length
Nivolumab	None	240 mg	Intravenous	Days 1, 15	28 days
Lenalidomide	None	15 mg*	Oral	Days 1-21 of	

CONFIDENTIAL

This document is confidential. Do not disclose or use except as authorized.

				each cycle	
--	--	--	--	------------	--

* If patient was dose reduced during the induction phase for lenalidomide below 15mg, then maintenance phase starts at that dose reduction and not at the higher 15 mg dose.

** During maintenance, if a patient experiences biochemical progression ($\geq 25\%$ increase and an absolute increase of $\geq 0.5\text{g/dL}$ from their nadir in their serum or urine m-spike or FLC with no CRAB features attributable to MM progression) high-dose dexamethasone may be re-added to the combination at a dose of 40mg oral given on days 1, 8, and 15 of a 28 day cycle after discussion with the overall PI.

The participant will be requested to maintain a medication diary. The medication diary should be returned to clinic staff at the end of each cycle.

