9. BIOMARKER, CORRELATIVE, MRD ASSESSMENT AND SPECIAL STUDIES

The mandatory correlative studies will consider several potential predictive biomarkers. As discussed in the appropriate sections of the protocol, mutations such as N-RAS, K-RAS, MYC up-regulation, and gain or loss of chromosome 1q or 1p are hypothesized to correlate with disease progression. The sample size of this phase-2 study, 41 patients, will allow exploratory analyses on TTP correlation with biomarkers. The number of biomarkers and the associated

CONFIDENTIAL

This document is confidential. Do not disclose or use except as authorized.

multiplicities will only allow us to provide empirical point estimates and confidence intervals for TTP-biomarker concordance indexes.

Please refer to Appendix B for a full sample collection table. This trial will provide samples from consenting SMM patients treated with Nivolumab, lenalidomide and dexamethasone to comprehensively characterize the MM genome and immune cells function and define molecular events driving development and progression of MM.

We will attempt to obtain samples on all patients at several time points during the study, including before therapy, at the end of cycle 6, at the time of response determination (CR), at disease relapse, and at the time of completion of the study. It is anticipated that approximately 90% of samples collected will be adequate for sequencing studies proposed.

The tumor cells will be collected as described below. From these samples, high quality DNA (for tumor cells) and RNA (for tumor cells and immune cells) for both exome sequencing and RNA sequencing will be obtained. Germline DNA will be also obtained from a buccal swab from all patients at any time point of the study. Samples collected for the purpose of research at Dana Farber Cancer Institute will be banked and retained for research use indefinitely.

Peripheral blood and bone marrow derived mononuclear cells will undergo immunologic assessments to assess the impact of therapy on general measures of cellular immunity, MM reactive T cells, and antigen specific immunity. The percentage of circulating and bone marrow derived regulatory immune cells will be determined.

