13.2 Sample Size, Accrual Rate and Study Duration

A total of 41 patients will be enrolled. We expect 1.5 years of active accrual (approximately 2 patients per month) and 3 years of follow-up of patients.

The final analyses of progression-based endpoints, such as estimating the 2-year progression-free rate and estimating the TTP distribution, will be conducted at the end of the study, which will occur after either all subjects have progressed or died or 2-years after the initiation of therapy of the last subject enrolled, whichever occurs first.

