13.5 Stopping Rule for Safety

All participants will be evaluable for treatment-related toxicity from the time of therapy initiation. The serious adverse event (SAE) for this purpose is defined as any grade 4 or higher unexpected, adverse event that is assessed as being related to the study intervention.

The following table provides the probabilities of observing 3 or more SAEs after the 20th patient and before the 40th patient. For example, with 20 participants, there is 0.60 probability of observing 3 or more SAEs if a true

CONFIDENTIAL

This document is confidential. Do not disclose or use except as authorized.

Local Protocol #: 16-242

Version Date: 23 January 2018

rate is 15% and the probability is 0.021 if a true rate is 3%.

True SAE rate	1%	3%	5%	10%	15%	20%	30%
Probability (\geq SAEs)	0.001	0.021	0.075	0.32	0.60	0.79	0.96

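### Accrual was closed in September 2017, but Section 13 still plans 41 patients and decides at 24 of 39; the stated error rates hold only if exactly 39 patients are eligible, and the plan gives no rule for any other number.

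*Combined protocol and SAP*

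**What the plan says.** On the hold, Section 1.1 states that, as of September 2017, "all patients are to discontinue nivolumab indefinitely, and no additional patients will be accrued to the trial". Section 5.1 repeats that "no additional patients will be accrued to the trial". This is current text and not an amendment log: the page header within Section 13.5 reads "Version Date: 23 January 2018".

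On size, the same version keeps the planned number throughout:

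- Protocol Summary: "Number of Patients: 41".
- Section 1.2: "A total of 41 patients will be included on this study".
- Section 9: "The sample size of this phase-2 study, 41 patients, will allow exploratory analyses on TTP correlation with biomarkers".
- Section 13.2: "A total of 41 patients will be enrolled. We expect 1.5 years of active accrual (approximately 2 patients per month").

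On the decision, Section 13.1 sets a single-stage design with 39 eligible patients out of 41 accrued. A 2-year progression-free rate of 50% is unpromising and 70% is promising. The rule is "If 24 or more of the 39 eligible patients are progression free at 2 years (observed rate of 62%), we will conclude" that further study is warranted, with exact binomial error rates of 0.10 and power above 0.9.

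Section 13.1.1 analyses the primary rate as a binomial proportion with a 90% confidence interval and gives no decision criterion. Section 13.1.2 applies a threshold of at least 62% to a secondary analysis of patients who did not receive cyclophosphamide (CTX) for mobilization, again starting from 39 eligible. No section gives the number enrolled, treated or eligible when accrual closed, and none says what decision applies if that number is not 39.

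**The concern.** A single-stage binomial rule is a pair: a count and a denominator. Its error rates belong to that pair. Once accrual is closed the denominator is fixed by events, yet the plan keeps the count and the error rates for the planned one. If the number eligible is not 39, the analyst must choose among a literal count of 24, a proportion near 62%, or a newly derived cut. These can give different answers on the same data.

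The choice would not be blind. The trial has one arm, and footnote 17 of the study calendar (Section 10) requires a response assessment at every Day 1 from Cycle 2. A rule chosen after closure would therefore be chosen while outcomes are visible. What is at stake is the formal conclusion that the combination warrants further study.

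**Working it through.** **Inputs.** From Section 13.1: p0 = 0.50, p1 = 0.70, n = 39 eligible, cut r = 24. From Sections 13.1 and 13.1.2: CTX share 5–20% of 39. The number eligible at closure is not given, so it is treated as an assumption and varied.

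**Formula.** For a rule of r or more successes in n, type I error is P(X ≥ r) with X ~ Binomial(n, 0.50), and power is the same tail with Binomial(n, 0.70).

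**Step 1: the plan's own figures.** At n = 39 and r = 24, type I error is 0.0998 and power is 0.906. Both match Section 13.1. Also 24/39 = 61.5%, printed as 62%, and 39/0.95 = 41.05, printed as 41.

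**Step 2: keep the count of 24 at another n.**

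| Eligible n | Type I error | Power |
|---|---|---|
| 30 | 0.001 | 0.160 |
| 35 | 0.021 | 0.652 |
| 37 | 0.049 | 0.807 |
| 38 | 0.072 | 0.863 |
| 39 | 0.0998 | 0.906 |
| 40 | 0.134 | 0.937 |
| 41 | 0.174 | 0.959 |

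At 23 or fewer the count cannot be reached. Below 39 the type I error never exceeds 0.072; above 39 it exceeds 0.10.

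**Step 3: can another cut restore both error rates?** For each n, take the smallest cut with type I error at or below 0.10.

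| Eligible n | Cut | Type I error | Power |
|---|---|---|---|
| 20 | 14 | 0.058 | 0.608 |
| 30 | 20 | 0.049 | 0.730 |
| 35 | 22 | 0.088 | 0.865 |
| 37 | 23 | 0.094 | 0.887 |
| 38 | 24 | 0.072 | 0.863 |
| 40 | 25 | 0.077 | 0.885 |
| 41 | 26 | 0.059 | 0.862 |

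Over n = 10 to 38 the best power is 0.887, at n = 37. No cut at any of these sizes, nor at 40 or 41, gives type I error at or below 0.10 together with power above 0.9. Only n = 39 does.

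**Step 4: does the 62% in Section 13.1.2 fill the gap?** It is defined for 80–95% of 39, that is 0.80 × 39 = 31.2 to 0.95 × 39 = 37.05 patients. At n = 32, 20/32 = 62.5% satisfies the threshold, but its type I error is 0.108, above the less than 10% claimed there. A percentage does not fix the error rate as n changes.

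**Step 5: interval width.** Section 13.1.2 gives a maximum exact 90% interval width of 28% at 39. The Clopper-Pearson maximum is 28.1 points at 39, which agrees after rounding, 28.5 at 38, 32.2 at 30 and 39.6 at 20.

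**The case against.** The strongest case against is that the harm is entirely conditional. No section says how many patients were eligible in September 2017. If it was exactly 39, the rule is intact and only stale accrual wording remains. This stands, and it limits the point to a gap in the plan and not a demonstrated loss.

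Second, the interval analysis in Section 13.1.1 is usable at any n. This also stands, and that analysis is not in question. But it carries no go/no-go criterion, so the conclusion about further study rests on Section 13.1 alone.

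Third, a design justification may be left in place as a record of what was planned, with the number treated reported with the results. That is defensible for the planned size. It does not tell the analyst whether the 24-of-39 rule still governs.

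Two stronger readings are tempting. A reader might infer that stopping early inflates false positives. The primary rule is stated as a count, and below 39 that count is conservative; inflation arises only at 40 or 41, or if a rounded percentage is carried over to a primary analysis for which no section prescribes it. A reader might also infer that the trial fell short of its target and can no longer reach a decision. The documents give no accrued number, so neither follows.

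**Conclusion.** The point holds in conditional form and should be fixed. The textual conflict is certain: one version both closes accrual and plans 41 patients with 1.5 years of active accrual. The 24-of-39 calculation itself is correct.

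The size of the consequence depends on the number eligible at closure. At exactly 39 there is none beyond wording. Below 39 the cost is power, modest at 38 and severe by 30. At 40 or 41, both possible under a plan to accrue 41, the cost is type I error. It would therefore be wrong to assume that reaching 39 or more leaves the rule safe. These figures rest on the plan's own 50% and 70% rates and on exact binomial tails; every n other than 39 is an assumption.

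**What to change.** In the Protocol Summary and Sections 1.2, 13.1 and 13.2, state the numbers treated and eligible when accrual closed, and remove the expectation of further accrual. Keep the 24-of-39 rule only if exactly 39 are eligible. Otherwise do one of the following.

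- **(A)** Withdraw the go/no-go claim and report the 2-year rate with its 90% interval, naming the interval as exact. Section 13.1.1 already largely plans this.
- **(B)** State the cut as a count with its exact type I error and power for the actual n, for example 14 of 20 (0.058, 0.61), 22 of 35 (0.088, 0.865), 25 of 40 (0.077, 0.885) or 26 of 41 (0.059, 0.862). Disclose that the cut was set while single-arm outcomes were accumulating.

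In Section 13.1.2, restate the maximum interval width and the base number for the CTX analysis at that n.

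The cost is amendment wording, with no new data. The downside is real: (A) gives up the formal decision, and (B) accepts stated power below 0.9 and a cut that was not set blind to outcomes.
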